8.2.1 General

The subjects will be described and summarised using the collected baseline demographic and medical variables which include but are not limited to age, gender, ethnicity, medical and medication history, diagnostic factors.

Primary and secondary endpoints will be evaluated using listings and appropriate summary statistics. The summary statistics for both primary and secondary outcomes will be reported together with a 95% confidence interval to assess the degree of precision in the estimates.

Summary statistics for baseline data, primary and secondary endpoints will be given according to the nature of the variable, continuous or categorical. For categorical variables, the number of observations, mean, standard deviation, median, minimum, and maximum will be presented, while for categorical variables the number of observations, frequency, and percentages will be reported.

All statistical tests will be exploratory in nature as the study is not powered for any statistical testing. Appropriate parametric and/or non-parametric analyses will be chosen for statistical analysis. Test of association for the table of counts will be based on the Fisher's Exact Test unless otherwise inappropriate. The exploratory analysis of continuous variables will be done using t-test if appropriate. The Wilcoxon rank-sum test will be explored if the data is non-normal. All statistical tests will be considered at 5% significance level.

All statistical analyses and calculation of confidence intervals will be performed using SAS software.

8.3 Efficacy Analysis

The primary objective of this study is to provide safety data for the SMF Short Modular Femoral Stem Hip System up to a follow up period of 20 years post implant. The indicators of efficacy of hip arthroplasty with the SMF Short modular femoral stem will be evaluated through the analysis of primary and secondary endpoints. For all continuous endpoints, 95% confidence intervals (CI) for the means will be reported.

8.3.1 Analysis of Primary Endpoint

- Safety assessment of the SMF Short Modular Femoral Stem implanted Subjects using Metal Ion Analysis and MARS MRI/ or CT at Baseline and at protocol scheduled visits at the 1 yearly or at the 3 yearly time point as per the study schematic Table 1.

Metal Ion Level assessment

- All Subjects at Baseline and every three years afterwards will have whole blood collected for metal ion testing of whole blood cobalt and chromium
- Symptomatic subjects with pain, swelling, and/or functional limitations if assessed by the PI to be related to the implant will have whole blood collected for metal ion testing of cobalt and chromium annually

The concentration levels of cobalt and chromium will be summarized using mean, median, SD, minimum and maximum at all recorded time points for all subjects. The results will be further categorized as subjects with pain, swelling and functional limitations. An exploratory ANOVA model will be fitted to evaluate any variation in changes over time.

MARS MRI/CT

- Subjects with whole blood cobalt and/or chromium > 7 ppb will have MARS MRI (or CT if MRI is contraindicated) performed

Based on the MARS MRI/CT results, a binary variable will be used to categorize subjects with blood cobalt and/or chromium > 7 ppb or below at all recorded time points. The frequencies together with percentages will be reported. The results will be further categorized as subjects with pain, swelling and functional limitations.

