3.0 Study Design

This is a single arm, consecutive series study to collect relevant clinical, laboratory and radiological data in up to 26 subjects, who have been implanted with the SMF Short Modular Femoral Stem THA system at 1 site in Australia.

The Baseline visit will be determined as the first visit to site after Ethics approval for the study has been received. This will be approximately 8-9 years post implant. Enrolled subjects will be followed up to 20 years post SMF implant. The Baseline visit assessments are described in Section 5.5 and 5.6. Post Baseline, the study will allow for metal ion assessments every 3 years for asymptomatic subjects and annual assessments for subjects with pain, swelling, and/or functional limitations if assessed by the Principal Investigator to be related to the SMF implant, having ruled out all other probable causes for the subject. If the subject has elevated whole blood cobalt or chromium (defined as >7ppb) a MARS MRI or CT will be obtained. These types of imaging techniques are aimed at

detecting inflammatory degenerative evolution of periarticular soft tissues including pseudo-tumors. A functional Questionnaire, HOOS JR Questionnaire will be completed at all patient site visits.

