3.1 Primary Endpoint

- Safety assessment of the SMF Short Modular Femoral Stem implanted Subjects using Metal Ion Analysis and MARS MRI/ or CT at Baseline and at protocol scheduled visits at the 1 yearly or at the 3 yearly time point as per the study schematic Table 1.

Metal Ion Level assessment

- All Subjects at Baseline and every three years afterwards will have whole blood collected for metal ion testing of whole blood cobalt and chromium
- Symptomatic subjects with pain, swelling, and/or functional limitations if assessed by the PI to be related to the implant will have whole blood collected for metal ion testing of cobalt and chromium annually

MARS MRI/CT

- Subjects with whole blood cobalt and/or chromium > 7 ppb will have MARS MRI (or CT if MRI is contraindicated) performed

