5.5.1 Baseline Visit

- Informed Consent
- Implant and Joint Status
- Operative Date
- Demographics
- Medical History and Concomitant Medication
- HOOS JR Questionnaire
- Radiographic evaluation
- Adverse events assessment
- Metal Ion Level assessment
 - Whole blood will be collected for metal ion testing of cobalt and chromium
- MARS MRI/CT
 - Subjects with whole blood metal ion levels > 7 ppb will have a MARS MRI performed (or CT if the MRI is contraindicated)
- Study termination, if applicable

5.5.2 1 Year/3 Year Visits (\pm 3M) up to 20 years post implant Follow Up

Annual visit schedule for symptomatic subjects and 3 Year visit schedule for non-symptomatic subjects

- Implant Status

- Demographics
- Medical History and Concomitant Medication
- HOOS JR Questionnaire
- Radiographic evaluation
- Adverse events assessment
- Metal Ion Level assessment
 - Whole blood will be collected for metal ion testing of cobalt and chromium
- MARS MRI/CT
 - Subjects with metal ion levels > 7 ppb will have a MARS MRI performed (or CT if MRI is contraindicated)
- Study termination, if applicable

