5.6 Table 1: Study Schematic

The intervals and schedule of events for this study are provided in Table 1.

Schedule of events	Screening/ Telephone Call	Baseline Visit	1 Year visit for symptomatic subjects/3 Year visit for non-symptomatic subjects (± 3M)	EOS Visit (20 years post SMF Implant procedure) (± 6M)	Unscheduled visit
Subject Status verification	X ¹				
Informed Consent		X			
Inclusion/Exclusion Criteria		X			
Implant Status	X ¹	X	X	X	X
Operative Date		X			
Demographics		X			

Schedule of events	Screening/ Telephone Call	Baseline Visit	1 Year visit for symptomatic subjects/3 Year visit for non-symptomatic subjects (\pm 3M)	EOS Visit (20 years post SMF Implant procedure) (\pm 6M)	Unscheduled visit
Medical History and Concomitant Medication		X	X	X	X
HOOS JR Questionnaire		X	X	X	X
X-ray Assessments		X ²	X ²	X ²	X ³
Adverse Events Assessment		X	X	X	X ³
Metal Ion level Assessments		X	X	X	X ³
MARS MRI /CT		X ³	X ³	X ³	X ³
End of Study		X ³	X ³	X	X ³

X¹ Verification of Eligibility via telephone contact to determine patient and implant status

X² X Ray Assessments/Radiographs will be in line with standard of care

X³ If Applicable

HOOS JR: The Hip Osteoarthritis Outcomes Score Junior is a validated short questionnaire that the patient completes focusing on joint pain, stiffness, and function relating to daily living.

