8.2 Statistical Design

A Statistical Analysis Plan (SAP) will be written and finalized prior to database lock. The following is a brief description of the analyses to be described in this plan. The SAP will be more detailed and account for all analyses.

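### The all-subject cobalt and chromium summaries alternate between the full cohort and a symptom-selected subset, because only symptomatic subjects are sampled at most annual visits

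*Combined protocol and SAP*

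**What the plan says.** Sampling depends on symptom status. Sections 3.1 and 8.3.1 have every subject give whole blood at Baseline and every three years. Subjects with pain, swelling or functional limitation that the investigator relates to the implant "will have whole blood collected for metal ion testing of cobalt and chromium annually". Section 5.5.2 sets the visits in the same way: "Annual visit schedule for symptomatic subjects and 3 Year visit schedule for non-symptomatic subjects". Table 1 adds ion testing for everyone at EOS. It also allows ion testing, where applicable, at unscheduled visits.

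Two anchors are used. Routine visits are counted from Baseline, of which Section 3.0 says "This will be approximately 8-9 years post implant". EOS is fixed at 20 years after implantation. Table 1 gives collection windows of 3 months either side for routine visits and 6 months either side for EOS.

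On analysis, Section 8.3.1 says the "concentration levels of cobalt and chromium will be summarized using mean, median, SD, minimum and maximum at all recorded time points for all subjects". It adds a breakdown by symptoms and then: "An exploratory ANOVA model will be fitted to evaluate any variation in changes over time". It also reports the percentage of subjects above 7 ppb at every recorded time point. Section 8.3 adds: "For all continuous endpoints, 95% confidence intervals (CI) for the means will be reported". Section 8.2 calls the description brief and says of the later plan: "The SAP will be more detailed and account for all analyses".

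**The concern.** Section 8.3.1 does not limit the all-subject summary to visits at which all subjects are due. If the rule is followed as written, a row for a 3-yearly visit describes the cohort. The next two annual rows carry the same label but describe only subjects chosen because they have symptoms. If ion levels differ between symptomatic and other subjects, the series rises and falls with the visit schedule, not with any change in the patients.

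This is the main quantitative summary of the primary endpoint, and description is the purpose of the study. A reader could take the pattern as movement in ion levels over time. The percentage above 7 ppb changes denominator in the same way. The ANOVA sentence does not say which visits enter or how repeated samples from one subject are handled, so the same pattern may or may not carry into it.

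**Working it through.** **1. Schedule (inputs: Sections 3.0, 3.1 and 5.5.2, Table 1).** Follow-up after Baseline is 20 - 8 = 12 years or 20 - 9 = 11 years, which agrees with the synopsis figure of approximately twelve years.

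| Baseline (years post implant) | All subjects due (years after Baseline) | Symptomatic only | Count |
|---|---|---|---|
| 8 | 0, 3, 6, 9, 12 (= EOS) | 1, 2, 4, 5, 7, 8, 10, 11 | 8 of 12 |
| 9 | 0, 3, 6, 9, 11 (= EOS) | 1, 2, 4, 5, 7, 8, 10 | 7 of 11 |

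EOS therefore falls at post-Baseline year 11 for some subjects and 12 for others. If results were filed by years since Baseline, the year-11 row would combine complete EOS data from one group with symptomatic-only data from the other. With Baseline at 8.5 years, a symptomatic subject's year-11 visit falls at 19.5 years, the edge of the EOS window. Nothing says how to assign it.

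**2. Shift in the pooled mean.** Let m be the arithmetic mean in non-symptomatic subjects, m + d in symptomatic subjects, and s of 26 symptomatic throughout, with no change over time and no attrition.
- Full-cohort visit: m + (s/26) x d
- Symptomatic-only visit: m + d
- Difference: (1 - s/26) x d

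The documents give neither s nor d, so these are assumptions. With m = 2 ppb, s = 5 and d = 3 ppb, the mean is 2 + (5/26) x 3 = 2.58 ppb at full visits and 5.00 ppb otherwise, a shift of 2.42 ppb. Over s = 3 to 13 and d = 1 to 5 ppb, the shift runs from 0.50 ppb (s = 13, d = 1) to 4.42 ppb (s = 3, d = 5). It is zero if d = 0.

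A skewed case: 6 symptomatic subjects with geometric mean 4.0 ppb, the others 1.5 ppb, and log-SD 0.7 between and 0.3 within subjects. Arithmetic mean = geometric mean x exp((0.49 + 0.09)/2) = geometric mean x 1.336, giving 5.35 and 2.00 ppb, so d = 3.34. The shift is (20/26) x 3.34 = 2.57 ppb, from 2.78 to 5.35 ppb.

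**3. Percentage above 7 ppb.** Suppose two subjects exceed 7 ppb and both are symptomatic. The figure is 2/26 = 7.7% at full visits. Between them it is 2/13 = 15.4% with 13 symptomatic and 2/3 = 66.7% with 3.

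**4. What the confidence interval shows.** The half-width in SD units is t(0.975, n-1)/sqrt(n): 0.40 at n = 26, 1.05 at n = 6 and 2.48 at n = 3.

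**5. The exploratory ANOVA.** Illustrative simulation at the nominal 5% level: no true change; 4, 6 or 8 of 26 symptomatic throughout; symptomatic geometric mean 3 to 6 ppb against 1.5; log-SDs as above; Baselines split 13/13 between 8 and 9 years; time counted from Baseline. There were 1,500 trials per setting (4,000 for the levels row).

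| Analysis | False rejection |
|---|---|
| Change from Baseline, log scale | 0.9-2.5% |
| Change from Baseline, raw scale | 3.1-27.4% |
| One-way ANOVA on raw levels by visit | 19.2-85.5% |
| Subject + visit, all values, log / raw | 3.7-5.5% / 6.7-44.5% |
| Subject + visit, common visits only, log / raw | 3.9-5.8% / 2.6-4.0% |

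With no difference between symptomatic and other subjects, the ANOVA on levels rejects at most 3% of the time. Whether the artefact reaches the ANOVA therefore depends on choices that Section 8.3.1 leaves open.

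**The case against.** **The time axis is set.** A reader might infer that no time axis exists. The documents do not support that. The first bullet of Section 8.3.1 ties the assessment to the scheduled visits in Table 1, and all-subject sampling is counted from Baseline. Nothing proposes analysis by years since implant. What remains is narrower: EOS has a different anchor from the other visits, and no analysis windows reconcile the two.

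**The ANOVA concerns changes.** A reader might also take the 19-86% in the levels row as the plan's error rate. That goes too far. The text speaks of changes over time, nothing commits to a one-way ANOVA on raw levels, and Section 8.2.1 promises appropriate methods. On log change the problem nearly disappears. The gap that stands is that scale, visits and repeated samples are not specified, and raw change can still be inflated.

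**The reader is warned.** The symptom breakdown, numbers of observations, listings and confidence intervals would all show a drop from 26 to a handful of subjects. This is a real mitigation, but a partial one. The breakdown is additional to the pooled rows, gives no rule for a subject whose status changes, and is not said to enter the ANOVA.

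**The SAP will settle it.** For the model details this is fair. The pooled summary is different, because it is already a stated rule that a faithful SAP would carry forward. Reading the phrase as meaning only that no subject is excluded produces the same rows.

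**The size is assumed.** This stands in full. Section 3.0 requires other probable causes to be ruled out, so few subjects may qualify as symptomatic, and their ion levels may not differ.

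**Conclusion.** The point holds. By the protocol's own schedule, 8 of 12 or 7 of 11 post-Baseline annual visits are symptomatic-only, while Section 8.3.1 summarises all recorded time points for all subjects. The pooled mean then moves by (1 - s/26) x d with no true change, and the percentages above 7 ppb change denominator with it. The visit counts and the formula follow from the documents, given annual visits from Baseline, 26 subjects and stable symptom status.

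The size in ppb does not follow from the documents. The 0.50 to 4.42 ppb range and the simulated rejection rates are illustrations under stated assumptions, and the effect vanishes if symptomatic subjects have the same levels as the rest. For the ANOVA, at most 3% false rejection on log change and 3-27% on raw change show why the choice should be written down. They do not show that the planned test is invalid.

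The study is descriptive and every test is exploratory. The consequence is a misleading description of the primary endpoint, not a wrong decision. It should be fixed in the SAP.

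**What to change.** In the SAP, before database lock:

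1. Give all-subject ion summaries and percentages above 7 ppb only at Baseline, 3, 6 and 9 years after Baseline, and EOS.
2. Put the annual symptomatic-only values in a separate table labelled as such, with n at each visit. List values from unscheduled visits.
3. State the analysis visit windows and treat EOS as its own visit, so that post-Baseline years 11 and 12 are not mixed with it.
4. Fit the exploratory time analysis on the common visits with a subject effect, on log concentration if the data are skewed. Whether slopes should also vary between subjects is a separate modelling choice.

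The cost is SAP wording and modest programming. The time model uses fewer values: with 6 symptomatic subjects and Baseline at 8 years, the common visits supply 26 x 5 = 130 of 130 + 6 x 8 = 178 values. The other 48 are still reported, in the separate table. No new data are needed, and neither sampling nor clinical care changes.

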Study Objective	The primary objective of this study is to provide safety data for the SMF Short Modular Femoral Stem Hip System up to a follow up period of 20 years post implantation
Primary Endpoint	Safety Data based on the following assessments: 
 ▪ Whole blood cobalt and chromium ion levels collected annually for symptomatic subjects and every 3 years for non-symptomatic subjects ▪ Metal artifact reduction sequence (MARS) magnetic resonance imaging (MRI) or Computed Tomography (CT) in subjects with whole blood cobalt and/or chromium > 7 parts per billion (ppb)
Secondary Endpoints	
 ▪ Standard of Care Radiographic assessments ▪ HOOS JR Hip Questionnaire ▪ Revision of any component of the study device for any reason ▪ Adverse events assessment
Length of Study	Approximately Twelve Years. Subjects have been implanted with the SMF Device in 2009 and 2010 at the investigational site. The Baseline visit will be determined as the first visit to site after Ethics approval for the study has been received. This will be approximately 8-9 years post implant. Enrolled subjects will be followed up to 20 years post SMF implant
Number of Sites	1 site (Australia)
Sample Size	Up to 26 subjects based on feasibility only
Inclusion Criteria	
 ▪ Subject has undergone primary total hip arthroplasty with the SMF Short modular femoral stem at the study site and still has the original implant at the time of Ethics Committee (EC) approval of the study ▪ Subject is willing and able to participate in follow-up visits at the study site

Exclusion Criteria	
 ▪ The Subject, in the opinion of the PI, has an emotional or neurological condition that would affect their ability or willingness to participate in the study including mental illness, mental retardation, drug or alcohol abuse ▪ Subject is known to be at risk for lost to follow-up or failure to return for scheduled visits
---------------------------	--

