8.5 Missing Data

A complete accountability report, along with the explanation for lost-to-follow-up, death, revision, and withdrawn subjects, will be provided in the Clinical Study Report (CSR). A complete list of the informative/non-informative missing data will be also be provided in the CSR. Due to the nature of the study, no imputation of missing data is planned.

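### Section 8.3.1 names an ANOVA for cobalt and chromium over time without a subject term, although the data are repeated, unequally spaced samples on at most 26 subjects; a mixed model should be named instead

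*Combined protocol and SAP*

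**What the plan says.** Section 8.3.1 summarises cobalt and chromium at each recorded time point, breaks the results down by symptoms, and adds one model: "An exploratory ANOVA model will be fitted to evaluate any variation in changes over time". It does not say whether the outcome is the level or the change from baseline. It also does not say which factors enter, what the error term is, or how annual and 3-yearly samples are combined.

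The data are repeated samples. Under section 3.1, "All Subjects at Baseline and every three years afterwards will have whole blood collected for metal ion testing". For symptomatic subjects whose symptoms are judged implant-related, 8.3.1 adds that they "will have whole blood collected for metal ion testing of cobalt and chromium annually". Section 3.0 sets the horizon: "Enrolled subjects will be followed up to 20 years post SMF implant". The synopsis gives the size: "Up to 26 subjects based on feasibility only".

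Section 6.1.7 stops study follow-up at revision. On missing data, section 8.5 says: "Due to the nature of the study, no imputation of missing data is planned". Section 8.2.1 sets the status of the tests: "All statistical tests will be exploratory in nature as the study is not powered for any statistical testing", and "All statistical tests will be considered at 5% significance level". Section 8.2 calls the statistical text brief and leaves detail to a SAP to be finalised before database lock. Nothing in section 8 mentions correlation between samples from one subject.

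**The concern.** Whether cobalt and chromium rise is central to a study whose sole aim is safety, and this ANOVA is the only model named for it. The word covers several analyses that behave differently on these data:

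- A one-way ANOVA by visit treats each sample as a different person, so stable differences between subjects inflate the error term for a within-subject effect.
- An ANOVA on changes from baseline, treated as independent, ignores that all changes in a subject share one baseline value.
- A complete-case repeated-measures ANOVA has a sound error term, but loses any subject who is revised, dies, is lost or misses a round.
- An ANOVA with subject as a factor, on all available rows, handles most of this.

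The plan does not choose among them. Loss may also relate to the outcome: revision ends follow-up, and section 1.0 says modular-neck patients may be at greater risk of revision. A pooled trend could then be too flat.

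**Working it through.** The plan has no figure to reproduce: 26 is a feasibility number, and no SD, within-subject correlation, expected rise or drop-out rate is given. Those inputs are assumptions below.

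**Samples per subject (sections 3.0, 3.1 and Table 1).** With baseline at year 8, 3-yearly rounds fall at 8, 11, 14, 17 and 20 (5 samples) and annual sampling gives 13. With baseline at year 9, rounds fall at 9, 12, 15 and 18, plus the end-of-study visit at 20 (5 samples), and annual sampling gives 12. If 5 of 26 subjects (19%) were sampled annually throughout, they would supply 5 × 13 = 65 of 65 + 21 × 5 = 170 samples, or 38%.

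**Error term with no true change.** Take n = 26, k = 5 common rounds, total variance σ² and intraclass correlation ρ, equal between all pairs of rounds.

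- Expected mean square for visit: σ²(1 − ρ).
- Expected residual mean square of a one-way ANOVA: σ²[kρ + (1 − ρ) + (k − 1)(1 − ρ)]/k = σ².
- The F ratio therefore centres near 1 − ρ instead of 1: 0.5 at ρ = 0.5 and 0.2 at ρ = 0.8.
- Simulated rejection at the 5% level (critical F on 4 and 125 df = 2.44): 0.2% at ρ = 0.5 and under 0.1% at ρ = 0.8. With a subject term it is about 5%.

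**Detection of a 1.5-fold rise, log-SD 0.8.** The rise is ln(1.5)/0.8 = 0.507 SD, taken as linear over the 5 rounds, so Σ(μⱼ − μ̄)² = 0.1605. With a subject term the noncentrality is λ = 26 × 0.1605/(1 − ρ) = 4.17/(1 − ρ), which is 8.35 at ρ = 0.5 and 20.9 at ρ = 0.8. The critical F on 4 and 100 df is 2.46. The one-way results are simulated.

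| ICC | True rise | One-way ANOVA | With subject term |
|---|---|---|---|
| 0.5 | 1.5-fold | 15–16% | 60% |
| 0.8 | 1.5-fold | 5% | 96% |
| 0.5 | 2-fold (0.866 SD) | 79% | 98% |
| 0.8 | 2-fold (0.866 SD) | 80% | >99.9% |

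At ICC 0 the two analyses agree (31% for a 0.5 SD rise), so the loss comes entirely from the ignored correlation.

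**ANOVA on changes from baseline, treated as independent.** The comparison between visits is again conservative (0.2–0.3% rejection with no change), but the test that the mean change is zero rejects about 21% of the time. The direction of error depends on the reading.

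**Drop-out.** Assumed: geometric mean 2 ppb, log-SD 1.0, ICC 0.8, 40% of subjects above 7 ppb leaving after each round, and 8% loss otherwise.

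- True 1.5-fold rise: the pooled trend estimates 1.21- to 1.24-fold over repeated simulation runs, a subject-factor ANOVA on all rows 1.54-fold, and a mixed model 1.50-fold.
- No true change: the pooled trend gives 0.83- to 0.85-fold.
- About 16 of 26 subjects have all five rounds. A complete-case repeated-measures ANOVA detects the 1.5-fold rise 56% of the time, against 83% for the mixed model.

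In a second setting (true slope 0.5 SD, exit after a value above a threshold), the pooled slope is 0.31, 0.16 and −0.05 when 10%, 23% and 41% are lost. The mixed model gives 0.49, 0.49 and 0.51. In both settings loss depends only on observed values, which favours the mixed model by construction.

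**The case against.** The strongest reply is that the protocol never says the ANOVA is one-way. Section 8.2.1 lets appropriate methods be chosen, and section 8.2 promises a fuller SAP. A reader might infer that the plan commits to a wrong error term. It does not: the text leaves the term unstated, and an ANOVA with subject as a factor on all rows is a legitimate reading that largely avoids both problems (1.54-fold estimated for a true 1.5-fold rise, detected in 88–90% of runs). That stands. What remains is that the protocol gives the SAP no direction on a choice that matters.

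A reader might also infer that real rises would go unnoticed. Even a one-way ANOVA finds a 2-fold rise about 80% of the time. Section 8.3.1 also reports levels and the frequency above 7 ppb at every time point, and section 8.2.1 adds listings and 95% confidence intervals.

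The drop-out figures rest on an assumed link. In the protocol a level above 7 ppb triggers imaging, not revision or withdrawal, and no departure rate is given. Bias is a credible risk of unknown size. The lack of imputation is not itself a fault, since a likelihood-based mixed model needs none when loss depends on observed values.

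Finally, 8.3.1 breaks results down by symptoms but does not plan a symptom factor in the model. Treating repeat samples as independent in such a test is a hazard to guard against, not a fault in the text.

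**Conclusion.** The point holds as under-specification with a better method available at almost no cost. Section 8.3.1 names an ANOVA for correlated, unequally spaced data and does not tie it to the subject. If samples were treated as independent, the by-visit test would be far too conservative for any substantial correlation, and the pooled trend would be too low if subjects with high levels leave. If only complete cases were used, subjects with a missing round would be lost.

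The directions follow from the design and the reading chosen. The sizes rest on assumed log-SD (0.8 or 1.0), ICC (0.5 to 0.8), a linear rise, 26 subjects, 5 common rounds and assumed drop-out.

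The documents do not support saying that the error term is wrong as written, that rises will be missed, or that the trend will be biased. The test is exploratory in a descriptive study, and no decision rule depends on it. This is a worthwhile improvement, not a must-fix.

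**What to change.** Replace the ANOVA sentence in 8.3.1, and carry the change into the SAP, with text to this effect: cobalt and chromium will each be analysed with a linear mixed model with a random subject effect and actual years since implantation as a continuous covariate, using all available samples in the stated analysis population. The log scale will be used if values are skewed, by a rule written beforehand. The change per 3 years will then be reported as a ratio with a 95% confidence interval. For scale, a 1.5-fold rise over the 12 years from year 8 to year 20 is 1.5^(1/4) = 1.11-fold per 3 years.

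Add three statements: any symptom comparison uses the same model, so repeat samples do not count as new subjects; the model assumes that loss depends on observed values; and a sensitivity analysis addresses loss after revision.

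The cost is a few sentences and one mixed-model procedure in SAS, with no new data. The analysis stays exploratory. The by-visit summaries are unchanged, and the model does not correct them for selective loss. The downside is reliance on the missing-at-random assumption, which the sensitivity analysis is there to probe.
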